## List of abbreviations

AE	Adverse event
ATC	Anatomical Therapeutic Classification
AUC	Area Under the Curve
bid	bis in diem/twice a day
CSR	Clinical Study report
CTC	Common Toxicity Criteria
CTCAE	Common Terminology Criteria for Adverse Events
DMC	Data Monitoring Committee
FAS	Full Analysis Set
eCRF	Electronic Case Report Form
IVR	Interactive Voice Response
IWR	Interactive Web Response
MedDRA	Medical Dictionary for Regulatory Activities
NCI	National Cancer Institute
o.d.	Once Daily
OS	Overall Survival
PFS	Progression-Free Survival
PK	Pharmacokinetics
PPS	Per-Protocol Set
PRO	Patient-reported Outcomes
qd	Qua'que di'e / once a day
QoL	Quality of Life
RAP	Report and Analysis Process
RECIST	Response Evaluation Criteria in Solid Tumors
SAP	Statistical Analysis Plan
SOC	System Organ Class
TFLs	Tables, Figures, Listings
WHO	World Health Organization

## 1 Introduction

OMB157C2301 (OMB112517) is a Phase III, open-label, randomized, multicenter trial to evaluate efficacy and safety of ofatumumab (OFA) maintenance treatment versus no further treatment in subjects with relapsed chronic lymphocytic leukemia (CLL) who have responded to induction therapy using a parallel design.

**Background:** The primary endpoint has been met at the protocol-defined interim analysis that was triggered after 187 events were observed (data cut-off date on June, 19 2014). OFA maintenance demonstrated a significant improvement in PFS ( $p < 0.0001$ ) as assessed by the investigator over Obs (OFA maintenance: median [mPFS] of 29.4 months, Obs: mPFS of 15.2 months; HR 0.50; 95% CI 0.38, 0.66). A 120 day Safety update has been performed (safety update data cut-off (28-Feb-2015)).

Then, a planned analysis has been performed based on efficacy and safety data collected up to 20-Feb-2017, the cut-off date when 280 PFS events or death occurred in the study. The analysis of PFS based on investigator-assessment showed an estimated 45% risk reduction in the OFA maintenance arm compared to the Obs arm (Hazard ratio: 0.55 with 95% CI: 0.43,0.70). The median PFS times (95% CI) are 34.17 months (29.70, 38.01) and 16.89 months (12.98, 20.37) respectively for OFA maintenance arm and Obs arm.

**Analysis Plan:** The current version of the statistical analysis plan (SAP) for the final analysis is based on data collected up to last patient last visit. All the analysis conventions will follow the previous SAP (published on 02-Jun-2017 and addendum on 11-Jan-2018). Final analysis of PFS was performed at protocol defined 280 events and will not be updated. The analysis results will be used for descriptive purpose only.

The population pharmacokinetic analyses [redacted] using the established PopPK model [GlaxoSmithKline Document Number [2012N156806\\_002](#)] will not be repeated, as the PopPK model takes into account data from Cycle 1 Week1, Cycle 1 week 9 and Cycle 4. The majority of this data was already available at the time of the data cut-off 19-Jun-2014 and described in the PopPK report [GlaxoSmithKline Document Number [2014N215557\\_00](#)] in the interim CSR.

In case psychometric validation of B-symptoms score and QLQ-CLL16 domain scores will be performed, this would be documented in separate document and will not be part of the final analysis CSR.

The table below contains the list of outputs that will be produced for this final analysis.

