2. OBJECTIVES

Primary objective:

[figure not shown]
- To evaluate PFS of subjects treated with ofatumumab maintenance treatment compared to no further treatment after remission induction in subjects with relapsed chronic CLL

Secondary objectives:

- To evaluate the improvement in response, improvement in response time to next CLL treatment and overall survival in subjects receiving ofatumumab maintenance compared to no further treatment
- To evaluate the PFS after next-line therapy and the time to progression after next-line therapy
- To evaluate the safety and tolerability in subjects with CLL receiving ofatumumab maintenance compared to no further treatment
- To evaluate the health-related quality of life in subjects with CLL receiving ofatumumab maintenance compared to no further treatment as assessed by changes in patient reported outcome (PRO) measures relative to baseline
- To evaluate prognostic marker correlation with clinical response in subjects with CLL receiving ofatumumab maintenance compared to no further treatment
- To evaluate ofatumumab pharmacokinetic parameters in subjects with CLL receiving maintenance ofatumumab every 2 months

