8.3.5. Key Elements of Analysis Plan

The final analysis will take place when the total number of events is reached in the study. An event is defined as when a subject has disease progression (PD) or death due to any cause during the study. All available data will be analyzed and the results will be presented in a report. Released data that are available from later visits will also be included.

Withdrawal

Subjects will be treated until disease progression or withdrawal from study treatment due to unacceptable adverse event(s), consent withdrawal or other reasons. All data up to time of withdrawal will be included in the analysis.

Subjects who are withdrawn prematurely from study treatment, but who are not withdrawn from the study at the time of analysis, will be included in the analysis, regardless of treatment duration.

Missing Data

Since the period of follow-up for any subject will be dependent on efficacy and toxicity, the duration of follow-up will vary among subjects. Consequently, there will be no imputation for missing data, with the exception of objective response. Treated subjects who do not have any response data will be assumed to be non-responders. Further details will be given in the Reporting and Analysis Plan (RAP).

Derived and Transformed Data

The evaluation of progression-free-survival will be determined by investigator assessment of response according to the IWCLL updated NCI-WG CLL criteria [Hallek, 2008].

Other Issues

Data from all participating centers will be pooled for the analyses. It is anticipated that subject accrual will be spread thinly across centers. Therefore, summaries of data by center would probably not be informative and will not be provided.

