#### **Disease Markers:**

- Minimal Residual Disease (MRD)

The number and percentage of subjects with positive and negative MRD will be provided at each timepoint. The proportion of subjects with negative MRD and positive MRD will be compared between treatment groups with the Cochran-Mantel-Haenszel test adjusting for stratification factors (response at entry, number of prior treatments and type of prior treatment). An analysis of the time to first MRD positivity for subjects who were MRD negative at baseline will also be provided using Kaplan-Meier methodology.

- B-cell monitoring

The change and percent change of  $CD5^+CD19^+$  and  $CD5^-CD19^+$  from baseline will be summarized to assess the treatment effect, to monitor the normal B-cell population, and to follow their recovery. In addition, frequency and percentage of subjects with complete B-cell depletion and near-complete B-cell depletion will be summarized. Complete B-cell depletion is defined as the absolute value of  $CD5^+CD19^+$  and  $CD5^-CD19^+$  both equal to zero cells/uL. Near complete B-cell depletion is defined as the sum of the absolute value of  $CD5^+CD19^+$  and  $CD5^-CD19^+$   $<5$  cells/uL.

Tables that will be provided are:

- Summary of  $CD5^+CD19^+$  counts over time
- Summary of  $CD5^-CD19^+$  counts over time
- Summary of  $CD5^+CD19^+$  change from baseline (counts and percentage)
- Summary of  $CD5^+CD19^+$  percent change from baseline (counts and percentage)
- Summary of  $CD5^-CD19^+$  change from baseline (counts and percentage)
- Summary of  $CD5^-CD19^+$  percent change from baseline (counts and percentage)
- Summary of subjects with complete B-cell depletion Summary of subjects with near-complete B-cell depletion
- Prognostic markers correlating with clinical response

Cox-regression will be used to explore the relationship between PFS and the following explanatory variables: treatment group, cytogenetics (analyzed by FISH) at baseline,

IgVH mutational status at baseline,  $\beta$ 2 microglobulin at baseline, baseline CD20 and baseline complement level. Ctau and Cmax at Cycle 1 Day 1, Cycle 1 Day 8, and Cycle 4 and cytogenetics at relapse may also be considered as possible explanatory variables in the model.

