## 1 Introduction

OMB157C2301 (OMB112517) is a Phase III, open-label, randomized, multicenter trial to evaluate efficacy and safety of ofatumumab (OFA) maintenance treatment versus no further treatment in subjects with relapsed chronic lymphocytic leukemia (CLL) who have responded to induction therapy using a parallel design.

**Background:** The primary endpoint has been met at the protocol-defined interim analysis that was triggered after 187 events were observed (data cut-off date on June, 19 2014). OFA maintenance demonstrated a significant improvement in PFS ( $p < 0.0001$ ) as assessed by the investigator over Obs (OFA maintenance: median [mPFS] of 29.4 months, Obs: mPFS of 15.2 months; HR 0.50; 95% CI 0.38, 0.66). A 120 day Safety update has been performed (safety update data cut-off (28-Feb-2015)).

Statistical Analyses Plan (SAP) for the current planned analysis is based on the efficacy and safety data collected up to 20-Feb-2017, the cut-off date when 280 PFS events or death occurred in the study. The analysis results will be used for descriptive purpose only. In particular supportive analysis to the primary endpoint will be provided.

All analyses that were done for the interim CSR (Dated 11-Sep-2014, Document # 2014N213614\_00) will be done for this analysis *except* the following outputs (see [Table 1](#)).

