**Table 1 Outputs not produced for analysis based on 280 PFS events**

Table	
1.8000	Summary of Covariates for Time to event Endpoints by Disease Score 2
1.8010	Summary of Study Treatment Status by Disease Score 2
1.8030	Summary of Subject Disposition at each study phase by Disease Score 2
1.8050	Summary of Demographic Characteristics By Disease Score 2
2.0180	Summary of Kaplan-Meier estimates of Investigator-Assessed Progression Free Survival by baseline Cytogenetics (FISH) Using 20% as the Cutoff
2.0181	Summary of Kaplan-Meier Estimates of Investigator-Assessed Progression Free Survival by Baseline Cytogenetics (FISH) using 12% as the Cutoff
2.0182	Summary of Kaplan-Meier Estimates of Investigator-Assessed Progression Free Survival by Cytogenetics (FISH) using 20% as the Cutoff
2.0183	Summary of Kaplan-Meier Estimates of Investigator-Assessed Progression Free Survival by Cytogenetics (FISH) at relapse Using 12% as the Cutoff

2.0190	Summary of Kaplan-Meier Estimates of Investigator Assessed Progression Free Survival by Baseline MRD status
2.1016	Summary of Kaplan-Meier Estimates of Investigator Assessed Progression Free Survival During the treatment phase and During Follow up
2.1017	Summary of Kaplan-Meier Estimates of Investigator-Assessed Progression Free Survival by Geographical Region
2.1018	Summary of Kaplan-Meier Estimates of Investigator Assessed Progression Free Survival for subjects who have completed 2 years of treatment or observations
2.1019	Summary of Kaplan-Meier Estimates of Investigator Assessed Progression Free Survival for Subjects who have only received 1 year of Treatment
2.2020	Summary of Improvement in ECOG performance Status
2.2031	Summary of Shifts from baseline in B-Symptoms by Disease Score 2
2.2040	Summary of Proportion of Subjects with no B-Symptoms Vs the Proportion of subjects with at least one B-Symptom Over Time
2.2050	Summary of CD5+ CD19+ (cells/uL) over time
2.2051	Summary of CD5- CD19+ (cells/uL) over time
2.2052	Summary of CD5+ CD19+ Change from Baseline over time
2.2053	Summary of CD5- CD19+ Change from Baseline over time
2.2054	Summary of CD5+ CD19+ Percent Change from Baseline over time
2.2055	Summary of CD5- CD19+ Percent Change from Baseline over time
2.2056	Summary of CD5+CD19+ Change from Baseline over time Excluding data After Taking Anti-Cancer Therapy
2.2057	Summary of CD5+CD19+ Percent Change from Baseline over time Excluding data After Taking Anti-Cancer Therapy

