2.2058	Summary of CD5-CD19+ Change from Baseline over time Excluding data After Taking Anti-Cancer Therapy
2.2059	Summary of CD5-CD19+ Percent Change from Baseline over time Excluding data After Taking Anti-Cancer Therapy
2.2060	Summary of Subjects with Complete B-cell Depletion
2.2064	Summary of Subjects with near-Complete B-cell Depletion
2.2070	Summary of Subjects with Positive and Negative Minimal Residual Disease (MRD) at each timepoint

2.2075	Summary of Subjects with Positive and Negative Minimal Residual Disease (MRD) at each Timepoint by Response at Entry
2.2080	Summary of Cox Proportional Hazards Regression Model For Relationship Between Investigator Assessed Progression-Free Survival and prognostic markers
2.4412	Summary of Kaplan-Meier Estimates of Overall Survival by IgVH Mutational Status 1 (collected)
2.4413	Summary of Kaplan-Meier Estimates of Overall Survival by IgVH Mutational Status 2 (97% cut-off)
2.4414	Summary of Cox Proportional Hazards Regression Models for Relationship between Overall Survival and Prognostic Markers (Univariate Models)
2.4415	Summary of Cox Proportional Hazards Regression Models for Relationship between Overall Survival Including IgVH Mutational Status 1 as One of the Covariates (Multivariate Model)
2.5010	Summary of KM Estimates of Investigator-assessed Progression-Free Survival After Next-Line Therapy Where Events of PD from the NTX eCRF (best response) Are also included and Taking Censored Death as an Event, for the ITT Population
2.5020	Summary of Best Response to First Next-Line Therapy
2.8000	Summary of Kaplan-Meier Estimates of Investigator-Assessed Progression-Free Survival by Disease Score 2 – High/Very High Risk
2.8005	Summary of Kaplan-Meier Estimates of Overall Survival by Disease Score 2 – High/Very High Risk
2.8020	Summary of Severity Scale Based on Selected Factors by Disease Score 2 – High/Very High Risk
2.8060	Summary of Kaplan-Meier Estimates of Time to Next Therapy Treating Death as an Event by Disease Score 2 – High/Very High Risk
2.8090	Summary of Kaplan-Meier Estimates of Sensitivity Analysis of Investigator-Assessed Progression-Free Survival Where Events Based on CT-scan are Included by Disease Score 2 – High/Very High Risk
2.8100	Summary of Kaplan-Meier Estimates of IRC-Assessed Progression-Free Survival by Disease Score 2– High/Very High Risk

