4.0150	Summary of Utility Score in EQ-5D by Treatment and Visit
4.0160	Summary of Change from Baseline Score in Utility Score in EQ-5D by Treatment and Visit
4.0200	Summary of Visual Analogue Scale (VAS) in EQ-5D by Treatment and Visit
4.0210	Summary of Change from Baseline in Visual Analogue Scale (VAS)

	in EQ-5D by Treatment and Visit
4.0250	Summary of Health Change Questionnaire by Treatment and Visit
Figures	
Figure No.	Title
Study Population	
11.0000	Graph of Percent Distribution of Age Group
Efficacy	
12.0010	Graph of Kaplan-Meier Investigator-Assessed Progression-Free Survival Curve
12.0020	Graph Of Kaplan-Meier Investigator-Assessed Progression-Free Survival Curve for the Per-protocol Population
12.0030	Graph of Kaplan-Meier Investigator-Assessed Progression-Free Survival Curve Including Events Based on CT-scan
12.0040	Graph of Kaplan-Meier IRC Assessed Progression-Free Survival Curve
12.0041	Graph of Kaplan-Meier Progression-Free Survival Based on Perceptives Sensitivity Analysis
12.0050	Graph of Kaplan-Meier Overall Survival Curve
12.0060	Graph of Kaplan-Meier Time to Next Therapy Curve
12.0070	Graph of Kaplan-Meier Investigator-Assessed Progression-Free Survival After Next-Line Therapy Curve
12.0080	Graph of Kaplan-Meier Investigator-Assessed Time to Progression After Next-line Therapy Curve
12.0090	Graph of Time to Response Assessment
12.0092	Graph of Kaplan-Meier Investigator-Assessed Time to Progression Curve
12.0100	Forest Plot of Hazard Ratios and 95% Confidence Intervals for Progression-Free Survival (Investigator-assessed, Investigator-Assessed including events determined by CT scan, IRC- Assessed with or without CT-scan)
12.0120	Forest Plot of Hazard Ratios and 95% Confidence Intervals for Investigator-Assessed Progression-Free Survival by Subgroups and Prognostic Markers
12.0121	Forest Plot of Hazard Ratios and 95% Confidence Intervals for Investigator Assessed Progression-Free Survival by Baseline Characteristics
12.0122	Forest Plot of Hazard Ratios and 95% Confidence Intervals for Investigator Assessed Progression-Free Survival by Prognostic Factors
12.0130	Graph of Hazard Ratio and 95% Confidence Intervals for Investigator-

	Assessed Progression-Free Survival Over Time
12.0140	Forest Plot of Hazard Ratios and 95% Confidence Intervals for Investigator Assessed Progression-Free Survival by Most Recent Type of Prior Chemoimmunotherapy and Best Response to Most Recent Type of Chemoimmunotherapy

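### The planned Cox model of PFS on prognostic markers is dropped at 280 events and not restored in the final analysis, so on the documents available it is run only on the 187-event interim data, with no reason given

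*SAP*

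**What the plan says.** Protocol section 2 lists this secondary objective: "To evaluate prognostic marker correlation with clinical response in subjects with CLL receiving ofatumumab maintenance compared to no further treatment". Under the matching heading on prognostic markers, protocol 8.3.5.1 and SAP 11.2 give one analysis: "Cox-regression will be used to explore the relationship between PFS and the following explanatory variables". The variables are treatment group and, at baseline, FISH cytogenetics, IgVH mutational status, beta-2 microglobulin, CD20 and complement. Protocol 8.3.5 fixes the timing: "The final analysis will take place when the total number of events is reached in the study". That number is 280.

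Two later plans follow the main SAP.

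- **280-event plan** (cut-off 20-Feb-2017). Its Introduction repeats "All analyses that were done for the interim CSR", apart from the exceptions in its Table 1, headed "Outputs not produced for analysis based on 280 PFS events". One exception is Table 2.2080: "Summary of Cox Proportional Hazards Regression Model For Relationship Between Investigator Assessed Progression-Free Survival and prognostic markers". Its Appendix 1 keeps Figure 12.0120, a forest plot of hazard ratios for "Progression-Free Survival by Subgroups and Prognostic Markers"; Figure 12.0122, a similar plot by prognostic factor; and Table 2.0020, the general Cox model for investigator-assessed PFS.
- **Final-analysis plan** (last patient last visit). Its Introduction says "Final analysis of PFS was performed at protocol defined 280 events and will not be updated". Its output list contains neither Table 2.2080 nor any other PFS model from randomization.

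Both later plans call their results descriptive.

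**The concern.** The analysis that the protocol attaches to a stated secondary objective falls between two lists. The 280-event plan drops it, and the final-analysis plan freezes PFS at 280 events, so it does not come back. Table 2.2080 appears as an exception to repeating the interim outputs, which implies that it was produced once, at the interim (cut-off 19 June 2014). The reported marker associations would then use 187 of the 280 planned events, although the full PFS data exist. At stake is the precision of an exploratory result, and whether a reader of the final report can tell which run answers the objective.

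**Working it through.** **1. Where the table appears**

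| Place | Table 2.2080 |
|---|---|
| Protocol 8.3.5.1; SAP 11.2 | Model planned |
| Interim report, 187 events | Produced, by implication of the 280-event plan's exception list |
| 280-event plan, Table 1 | Listed as not produced |
| 280-event plan, Appendix 1 | Absent |
| Final-analysis plan, output list | Absent |

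Four other secondary outputs on the 280-event exception list return in the final-analysis plan: 2.2020 (ECOG), 2.2052 and 2.2053 (B-cells) and 2.2070 (MRD). None of these is a PFS output, so the freeze on PFS did not affect them. The final-analysis plan explains why the population PK analysis is not repeated. It gives no explanation for the marker model.

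**2. What remains at 280 events**

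- Figures 12.0120 and 12.0122. Going by their titles, they are forest plots of PFS hazard ratios by marker or factor. Such plots normally show the treatment effect within marker groups, not the adjusted association of a marker with PFS.
- Table 2.0020. SAP 11.1 describes a stepwise model with entry and removal at 0.05 and only treatment forced in. Baseline cytogenetics is one example of a candidate. IgVH, beta-2 microglobulin and complement are not named there, nor in the covariate list in SAP 9.2.14.
- The Kaplan-Meier PFS tables by cytogenetics (2.0180 to 2.0183) and baseline MRD (2.0190) are dropped at 280 events too.

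**3. The plan's own event counts**

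Inputs from protocol 8.2.1: medians of 28 and 39.2 months, 1:1 allocation, two-sided 5%, 80% power. HR = 28/39.2 = 0.714.

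- Schoenfeld: 4 x (1.960 + 0.842)^2 / (ln 0.714)^2 = 278 events.
- Freedman: (1.960 + 0.842)^2 x [(1 + 0.714)/(1 - 0.714)]^2 = 283 events.
- Both agree with the stated 280. The interim at two thirds is 2/3 x 280 = 186.7, or 187.

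**4. Precision lost**

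- Events not used: 280 - 187 = 93, so 280 events are 93/187 = 50% more than the interim had.
- In theory SE is proportional to 1/sqrt(events). The ratio is sqrt(187/280) = 0.817, an 18% smaller SE at 280 events.
- From the treatment-effect intervals in the final-analysis plan, SE = ln(upper/lower)/(2 x 1.960). At 187 events, ln(0.66/0.38)/3.92 = 0.141. At 280 events, ln(0.70/0.43)/3.92 = 0.124. The ratio is 0.88, about 12% smaller.

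**5. Detectable marker hazard ratio**

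The documents give no marker prevalence, so a range is assumed: a binary marker with prevalence p, uncorrelated with the other covariates, D events, 80% power, two-sided 5%. Detectable HR = exp[(1.960 + 0.842)/sqrt(D p (1 - p))]. For p = 0.10 and D = 187 this is exp(2.802/sqrt(16.83)) = exp(0.683) = 1.98.

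| Assumed p | 187 events | 280 events |
|---|---|---|
| 5% | 2.56 | 2.16 |
| 10% | 1.98 | 1.75 |
| 20% | 1.67 | 1.52 |
| 30% | 1.56 | 1.44 |
| 50% | 1.51 | 1.40 |

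**The case against.** The strongest reply is that little is lost. The model is exploratory, carries no alpha and sits outside the tested hierarchy of time to next therapy and overall survival. It was run at the interim, where the primary endpoint was met and 479 evaluable subjects were available against 478 required. All of this stands, and it limits the point to precision and clarity.

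The reply also says that marker information does exist at 280 events. That stands in part. The objective compares the arms, and the planned Cox model lists no marker-by-treatment interaction. Forest plots of treatment effect by marker group would address that comparison where the model as written does not. They complement the model, though. They do not estimate the association of each marker with PFS, which is what the protocol planned. Their exact content is also inferred from titles, since no table shells are supplied.

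The final-analysis plan refers to an addendum of 11-Jan-2018 that cannot be identified in the supplied text. Whether it restored the table cannot be checked.

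The precision figures are best cases. The 18% is theoretical, and protocol 6.3.3 collects baseline markers only where possible, so the events with marker data may be fewer at both cut-offs.

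**Conclusion.** The point holds as a gap in the output lists. The planned marker model is not produced at 280 events, is absent from the final list, and no reason is given. Subject to the addendum, its only run uses 187 events. The cost is a standard error that could be 12% to 18% smaller. Equivalently, under the assumptions above, the detectable hazard ratio falls from 2.56 to 2.16 at 5% prevalence and from 1.51 to 1.40 at 50%. The primary conclusion, type I error and the two inferential secondary endpoints are unaffected.

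A reader might infer that the secondary objective cannot be answered, or that it rests on interim data alone. The documents do not support either reading: the interim run gives an answer, though a less precise one, and the 280-event list keeps two marker forest plots and a Cox model that may retain cytogenetics. Nor can one say that 187 events are too few for a particular rare marker such as 17p-, because no prevalence is given.

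**What to change.** Add Table 2.2080 to the output list and run it on the 280-event PFS data (cut-off 20-Feb-2017) with the baseline covariates of protocol 8.3.5.1. Label it descriptive, and state that this version, not the interim one, is the main analysis for the prognostic-marker objective. This does not conflict with freezing PFS, since it uses the frozen data. If the 11-Jan-2018 addendum already restores the table, or there was a reason to drop it, the final-analysis plan should say so.

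The cost is one extra exploratory table and no new data collection. The results may differ from the interim version, and the report would then have to present both. The documents do not say whether the interim program can be reused after the change of sponsor.
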